8.3 Pharmacodynamic Assessments

Not applicable.

8.4 Pharmacogenomic Assessments

Not applicable.

8.5 Biomarker Assessments

Not applicable.

Protocol 405-201-00037

8.6 Future Biospecimen Research Samples

Not applicable.

8.7 Safety Assessments

Safety assessments in this trial include AEs, clinical laboratory tests, physical examinations, vital signs, ECGs, and the C-SSRS.

Details pertaining to the definitions, collection, reporting, and follow-up of AEs are described in [Section 8.8](#).

8.7.1 Clinical Laboratory Assessments

Clinical laboratory samples will be collected at the time points described in the schedule of assessments ([Table 1.3-1](#)) to perform the clinical laboratory assessments described in [Section 10.2](#). Refer to [Section 10.5](#) for criteria for identifying laboratory values of potential clinical relevance.

The total volume of blood to be collected during the trial will be documented in the ICF and assent form. The central laboratory will be used for all laboratory testing required during the trial.

Subjects should be fasting for a minimum of 8 hours prior to the blood draws, if possible. Vital sign measurements and ECG assessments should be completed before any blood samples are collected. See exclusion criteria in [Section 5.2.2](#) based on screening laboratory tests. The results of these tests must be reviewed by the investigator prior to initiation of the administration of the IMP. Additional urine and blood samples may be collected for further evaluation of safety as warranted by the investigator's judgment. Reports from the central laboratory will be assessed by the investigator or qualified designee for clinical significance within the eCRF.

8.7.2 Physical Examination

A complete physical examination will be performed at the time points described in the schedule of assessments ([Table 1.3-1](#)). The complete physical examination will include height (screening only), weight, and calculation of body mass index (BMI) as well as assessment of the head, eyes, ears, nose, and throat; thorax; abdomen; skin and mucosae; neurological; and extremities. Directed physical examinations in response to reported AEs will be conducted as necessary.

Protocol 405-201-00037

Whenever possible, the same individual should perform all physical examinations for any individual subject throughout the course of the trial. Individuals performing the physical examination must be permitted to do so by local regulations, must be listed on the Food and Drug Administration (FDA) Form 1572 as principal investigator or subinvestigator, and must be listed on the trial site delegation of authority form as performing this function.

Any post-screening abnormalities considered by the investigator to be clinically significant are to be recorded as AEs on the AE eCRF.

8.7.3 Vital Signs

Vital signs (include systolic and diastolic blood pressure and heart rate) will be collected at the time points described in the schedule of assessments ([Table 1.3-1](#)). Subjects should be monitored for potentially clinically significant vital signs values ([Section 10.6](#)).

Blood pressure and heart rate measurements will be made in the supine and standing positions after the subject has been in each position for at least 3 minutes. The supine measurements will be performed first followed by the standing measurements.

8.7.4 Electrocardiogram

Electrocardiograms will be performed at the time points described in the schedule of assessments ([Table 1.3-1](#)). Subjects should be monitored for potentially clinically significant ECG results ([Section 10.7](#)). Any abnormalities considered by the investigator to be clinically significant are to be recorded as AEs on the AE eCRF.

The 12-lead ECGs will be performed in the supine position. Predose 12-lead ECGs conducted at check-in (Day -1 or Day 1) will be performed in triplicate, taken at least 1 minute apart following a 10-minute rest in the supine position. The average of the 3 values will be the baseline value. Based on the QTcF, a subject will be excluded if the correction is ≥ 450 msec for more than 1 of the 3 time points of triplicate predose ECGs performed for subjects < 12 years old or ≥ 460 msec for more than 1 of the 3 time points of triplicate predose ECGs performed for subjects ≥ 12 years old.

A central ECG service will be utilized for reading all ECGs in order to standardize interpretations for the safety analysis. In addition, ECG results will be evaluated at the trial site to monitor safety during the trial.

8.7.5 Suicidality Monitoring

Suicidality monitoring will occur at the time points described in the schedule of assessments ([Table 1.3-1](#)).

Protocol 405-201-00037

Suicidality will be monitored during the trial using the C-SSRS. The C-SSRS is a semi-structured interview that captures the occurrence, severity, and frequency of suicide-related thoughts and behaviors during the assessment period. The interview includes definitions and suggested questions to solicit the type of information needed to determine if a suicide-related thought or behavior has occurred. The interview and rating for the C-SSRS must be completed by a licensed clinician who has been successfully trained to rate this scale by the sponsor or a designee, and is medically responsible for the subject. Documentation of trial training should be maintained in the trial site's files.

The "Baseline/Screening" version of the C-SSRS will be completed at the screening visit and the "Since Last Visit" version of the C-SSRS will be completed at check-in (Day -1 or Day 1) and EoT/ET. There are required items to be completed, potential additional items if there is a positive response to a required item, and items for suicide/suicide behavior present during the interview. The C-SSRS uses dichotomous scales (ie, yes or no), Likert scales, and text or narrative to further describe the thoughts or behaviors.

8.7.6 Other Safety Variables

No other safety variables are applicable for this trial.

8.8 Adverse Events

8.8.1 Definitions

An AE is defined as any untoward medical occurrence in a clinical trial subject administered an IMP and which does not necessarily have a causal relationship with this treatment. Adverse events would not include information recorded as medical history at screening for pre-planned procedures for which the underlying condition was known and no worsening occurred. An adverse reaction is any untoward and unintended response to an IMP related to any dose administered.

A suspected adverse reaction is any AE for which there is a reasonable possibility that the IMP caused the AE. For the purpose of Investigational New Drug (IND) safety reporting, "reasonable possibility" means there is evidence to suggest a causal relationship between the IMP and the AE. Suspected adverse reaction implies a lesser degree of certainty about causality.

Treatment-emergent AEs (TEAEs) are defined as AEs with an onset date on or after the start of open-label treatment. In more detail, TEAEs are all AEs that started after the start of open-label IMP treatment; or if the event was continuous from baseline and was worsening, serious, IMP related, or resulted in death or discontinuation from the trial.

Protocol 405-201-00037

An SAE includes any event that results in any of the following outcomes:

- Death
- Life-threatening; ie, the subject was, in the opinion of the investigator, at immediate risk of death from the event as it occurred. It does not include an event that, had it occurred in a more severe form, might have caused death.
- Persistent or significant incapacity/disability or substantial disruption of the ability to conduct normal life functions.
- Requires inpatient hospitalization or prolongs hospitalization.
 - Hospitalization itself should not be reported as an SAE; whenever possible the reason for the hospitalization should be reported.
 - Hospitalizations or prolonged hospitalizations for social admissions (ie, those required for reasons of convenience or other nonmedical need) are not considered SAEs.
 - Prescheduled hospitalization to address a condition that has existed prior to the signing of the ICF and assent form should not be considered an SAE.
- Congenital anomaly/birth defect.
- Other medically significant events that, based upon appropriate medical judgment, may jeopardize the subject and may require medical or surgical intervention to prevent one of the outcomes listed above; eg, allergic bronchospasm requiring intensive treatment in an emergency room or home, blood dyscrasias or convulsions that do not result in hospitalization, or the development of drug dependency or drug abuse.

Nonserious AEs are all AEs that do not meet the criteria for a "serious" AE.

Adverse Events of Special Interest (AESIs): A noteworthy event for the particular product/IMP or class of products that a sponsor may wish to monitor carefully. All AESIs are to be reported as immediately reportable events (IREs).

Immediately Reportable Event (IRE):

- Any SAE
- Any AE related to occupational exposure
- Any AESIs (see [Section 8.8.5](#))
- Potential serious hepatotoxicity (see [Section 8.8.6](#))
- Pregnancies are also defined as IREs. Although normal pregnancy is not an AE, it will mandate trial discontinuation and must be reported on an IRE form and the Pregnancy Surveillance Form(s) to the sponsor. Pregnancy will only be documented on the AE eCRF if there is an abnormality or complication. This includes pregnancy of the subject or the partner of the subject.

Protocol 405-201-00037

Clinical Laboratory Test Value Changes: It is the investigator's responsibility to review the results of laboratory tests for each individual subject as they become available. This review will be documented by the investigator's dated signature on the laboratory report. The investigator may repeat the laboratory test or request additional tests to verify the results of the original laboratory tests. If this laboratory value is considered medically relevant (ie, clinically significant) by the investigator (subject is symptomatic, requiring corrective treatment or further evaluation), or if the laboratory value leads to discontinuation, and/or fulfills a seriousness criterion, this is considered an AE.

Severity: Adverse events will be graded on a 3-point scale and reported as indicated on the eCRF. The severity of an adverse experience is defined as follows:

- 1 = Mild:** Discomfort noticed, but no disruption to daily activity.
- 2 = Moderate:** Discomfort sufficient to reduce or affect normal daily activity.
- 3 = Severe:** Inability to work or perform normal daily activity.

IMP Causality: Assessment of causal relationship of an AE to the use of the IMP is defined as follows:

- Related:** There is a reasonable possibility of a temporal and causal relationship between the IMP and the AE.
- Not Related:** There is no temporal or causal relationship between the IMP and the AE.

8.8.2 Eliciting and Reporting Adverse Events

The investigator will regularly assess subjects for the occurrence of AEs. To avoid bias in eliciting AEs, subjects should be asked the nonleading question: "How have you felt since your last visit?" All AEs (serious and nonserious) reported by the subject must be recorded on the source documents and eCRF provided by the sponsor. Adverse event collection will begin after a subject signs the ICF and assent form.

Medical terminology should be used for AE reporting. Adverse events should be reported as a single unifying diagnosis whenever possible or, in the absence of a unifying diagnosis, as individual signs or symptoms.

Exacerbation or disease progression should be reported as an AE only if there are unusual or severe clinical features that were not present, or experienced earlier, or not expected based on the course of the condition.

Protocol 405-201-00037

An AE that undergoes a change in severity, seriousness, or toxicity should be reported as a new AE on the eCRF.

In addition, the sponsor must be notified immediately by telephone, fax, or e-mail of any IREs according to the procedure outlined below, in [Section 8.8.3](#). Special attention should be paid to recording hospitalization and concomitant medications.

The AE, start date (and start time, if possible), end date (and end time, if possible), seriousness, severity, relationship to trial treatment (IMP causality), action taken with trial treatment, and outcome will be recorded on the source documents and in the eCRF.

8.8.3 Immediately Reportable Events

The investigator must immediately report (within 24 hours), using an IRE form, after he/she or site personnel become aware of any IRE (SAE, AE related to occupational exposure, AESI, potential serious hepatotoxicity, or confirmed pregnancy), by telephone, fax, or e-mail to the sponsor or designee using the contact information on the cover page of this protocol (Please note that the IRE form is NOT the AE eCRF.).

8.8.4 Medical Device Incidents (Including Malfunctions)

Not applicable.

8.8.5 Adverse Events of Special Interest

Newly acquired skin eruptions that are nontraumatic will be considered AESIs. These may include, but are not limited to eruptions such as skin rashes, skin irritations, skin reactions, or acneiform lesions. This does not include localized contact irritation at ECG lead sites due to application/removal of lead adhesive.

Refer to the separate rash workup plan for complete details, including reporting forms, and extra measures that must be performed to characterize any skin AESI of a newly acquired skin eruption that is nontraumatic. The trial site will have a local designated dermatologist available for immediate consultation during the trial for these AESIs.

All AESIs should be reported as IREs (see [Section 8.8.3](#)).

8.8.6 Potential Serious Hepatotoxicity

For a subject who experiences an elevation in AST or ALT that is ≥ 3 times the ULN, a total bilirubin level should also be evaluated. If the total bilirubin is ≥ 2 times the ULN, complete an IRE form with all values listed and also report as an AE on the eCRF.

8.8.7 Procedure for Breaking the Blind

This trial does not use blinding procedures.

Protocol 405-201-00037

8.8.8 Follow-up of Adverse Events

8.8.8.1 Follow-up of Nonserious Adverse Events

Nonserious AEs that are identified at any time during the trial must be recorded on the AE eCRF with the current status (ongoing or resolved/recovered) noted. All nonserious events (that are not IREs) that are ongoing at the last scheduled contact will be recorded as ongoing on the eCRF. For any AE having been identified throughout the trial, during analysis, additional relevant medical history information may be requested by the sponsor to further ascertain causality (including, but not limited to, information such as risk-related behavior, family history, and occupation).

8.8.8.2 Follow-up of Immediately Reportable Events

This trial requires that subjects be actively monitored for IREs up to 7 (+ 2) days after dosing.

Immediately reportable events that are **identified or ongoing at the last scheduled contact** must be recorded as such on the AE eCRF page and the IRE form. If updated information (eg, resolved status) on IRE status becomes available after a subject's last scheduled contact, this must be reported to the sponsor and recorded on the AE eCRF page and the IRE form, according to the appropriate reporting procedures described in [Section 8.8.3](#).

It is expected that the investigator will provide or arrange appropriate supportive care for the subject and will provide prompt updates on the subject's status to the sponsor. The investigator will follow IREs until the events are:

- Resolved,
- Stabilized,
- The subject is lost to follow-up, or
- Has died.

Resolution means that the subject has returned to the baseline state of health and stabilized means that the investigator does not expect any further improvement or worsening of the subject's condition. The investigator will continue to report any significant follow-up information to the sponsor up to the point the event has resolved or stabilized, or the subject is lost to follow-up or has died.

Refer to [Section 10.3](#) for additional information regarding the follow-up period for subjects that become pregnant or for pregnant partners of male subjects.

Protocol 405-201-00037

8.8.3 Follow-up and Reporting of Immediately Reportable Events Occurring After Last Scheduled Contact

Any new IREs reported to the investigator which occur after the last scheduled contact and are determined by the investigator to be reasonably associated with the use of the IMP, should be reported to the sponsor according to the procedures outlined in [Section 8.8.3](#). This may include IREs that are captured on follow-up telephone contact or at any other time point after the defined trial period and continue to report any significant follow-up information to the sponsor until the events are resolved or stabilized, or the subject is lost to follow-up or has died.

8.9 Treatment of Overdose

For treatment of overdose, please refer to IB Section 6.4 (Overdose).

8.10 Subject Assessment Recording

Not applicable.

8.11 Other Assessments

8.11.1 Capsule Swallow Test

The ability of a subject to swallow the intact centanafadine XR capsule will be assessed during the screening period using a capsule swallow test. Based on this assessment, subjects will either be instructed to take the centanafadine capsules intact or the capsule contents sprinkled on a tablespoon of applesauce.

9 Statistical Considerations

9.1 Sample Size

Since this is an exploratory trial, no formal sample size calculations will be performed. Up to 12 subjects may be treated depending on the concentration data and the number of subjects completing through 24 hours.

Protocol 405-201-00037

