2.1 Trial Rationale

Currently, the PK of centanafadine administered as IR/XR capsules is being evaluated in adults. It is possible that the PK (particularly absorption) of centanafadine following administration of the XR formulation may be different in children as compared to adults due to physiological differences in the gastrointestinal tract. Therefore, the primary purpose of this trial is to evaluate the PK of centanafadine [REDACTED] following administration of centanafadine capsules in pediatric subjects (9 to 12 years, inclusive) with ADHD and determine if the XR formulation is appropriate for further evaluation.

[figure not shown]
[figure not shown]

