6.1 Trial Treatments Administered

Centanafadine will be supplied as 1 capsule containing a 50-mg dose as [REDACTED] beads and 1 capsule containing a 5-mg dose as IR beads for a total centanafadine dose of 55 mg. Both of the intact capsules or the capsule contents sprinkled on a tablespoon of applesauce will be taken orally in the morning [REDACTED]
[REDACTED] following a minimum 8-hour fast. [REDACTED]
[REDACTED]
[REDACTED]
[REDACTED]
[REDACTED]

The ability of a subject to swallow the intact capsules will be assessed during the screening period with empty capsules. Based on this assessment, subjects will either be instructed to take the centanafadine capsules intact or the capsule contents sprinkled on a tablespoon of applesauce. An attempt will be made to administer the intact capsules to approximately half of the subjects and approximately half of the subjects will be administered the capsule contents sprinkled on a tablespoon of applesauce.

[REDACTED]
[REDACTED]
[REDACTED]
[REDACTED]

For further information regarding the treatment period, including the follow-up period, see [Section 4.1](#).

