9.2 Datasets for Analysis

The PK dataset will include all subjects who receive the single dose of centanafadine and have at least 1 postdose evaluable plasma concentration.

The safety dataset will include all subjects who receive the single dose of centanafadine.

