9.4.3.2 Pharmacokinetic Analysis

A noncompartmental analysis will be performed. Plasma concentrations of centanafadine and metabolite(s) will be summarized by time point and mode of administration (intact capsules or capsule contents sprinkled on a tablespoon of applesauce). The PK parameters will be summarized by analyte and mode of administration using descriptive statistics.

No inferential statistical analysis will be conducted.

The following PK parameters will be summarized:

- Maximum (peak) plasma concentration (C_{max}) of centanafadine
- Time to maximum concentration (t_{max}) of centanafadine
- Area under the concentration-time curve from time 0 to 12 hours postdose (AUC_{0-12h}) of centanafadine

Protocol 405-201-00037

- [REDACTED]
- [REDACTED]
- [REDACTED]

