9.5 Interim Analysis and Adaptive Design

No interim analysis or adaptive design are applicable.

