This statistical analysis plan (SAP) documents the statistical methodology and data analysis algorithms and conventions to be applied for the analysis of clinical trial data of trial 405-201-00037 for centanafadine. The current version of SAP is based on protocol version 3.0 dated on 23 Jul 2019 and final SAP will be consistent with the final version of the protocol.

2 Trial Objectives

Primary Objectives:

To characterize the single-dose concentration-time profile from 0 to 12 hours of centanafadine in pediatric subjects (9 to 12 years, inclusive) with attention-deficit hyperactivity disorder (ADHD).

Other Objectives:

- To assess the safety and tolerability of centanafadine XR in pediatric subjects.
- To assess the ability of pediatric subjects to swallow the centanafadine XR capsule.
- [REDACTED]
- [REDACTED]
- To assess centanafadine concentrations 24 hours postdose for evaluation of the potential for accumulation following multiple doses.
- To compare the PK of centanafadine after administration of the intact capsules or the capsule contents sprinkled on to applesauce.

3 Trial Design

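### Does letting the number treated depend on the concentration data contradict the statement that there is no interim analysis or adaptive design?

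*Protocol*

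**What the plan says.** The size of the trial rests on a single sentence in Protocol 9.1, repeated word for word in the synopsis and in SAP section 4: "Up to 12 subjects may be treated depending on the concentration data and the number of subjects completing through 24 hours". It follows a disclaimer: "Since this is an exploratory trial, no formal sample size calculations will be performed". Protocol 9.5 says "No interim analysis or adaptive design are applicable", and Protocol 9.4.3.2 says of the pharmacokinetic (PK) analysis "No inferential statistical analysis will be conducted".

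Four other places bear on the point:

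- Protocol 9.2 admits to the PK dataset all dosed subjects who "have at least 1 postdose evaluable plasma concentration".
- Protocol 4.5 defines a completer as a subject who completes Day 2, and Protocol 5 lets the sponsor replace subjects who leave for reasons unrelated to safety.
- Protocol 2.1 says that the trial should "determine if the XR formulation is appropriate for further evaluation".
- On the two ways of giving the capsules, Protocol 6.1 says "An attempt will be made to administer the intact capsules to approximately half of the subjects", and SAP section 2 lists an objective "To compare the PK of centanafadine after administration of the intact capsules or the capsule contents sprinkled on to applesauce".

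**The concern.** The sample-size sentence names two things that decide how many children are treated: the concentration data, and the count completing 24 hours. Because completion is listed separately, the first item seems to add something to it. The natural suspicion is that someone looks at the concentrations part-way and decides whether to go on. That would be a data-dependent sample size, which Protocol 9.5 appears to rule out. Neither document gives, in its visible text, a minimum number, a time for such a look, or a criterion.

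Cmax, tmax and AUC0-12h are all computed from these concentrations. If enrolment stopped when early profiles looked tight, the reported spread would tend to be too small. If it stopped when they looked variable, the spread would tend to be too large. If it stopped on the level, the mean would shift in the direction of the rule. Since the results inform whether the XR formulation goes forward, a reader would want to know whether n was chosen after seeing the values.

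**Working it through.** **Is there a contradiction?** The plan gives no figure to reproduce: no alpha, power, effect size, standard deviation or precision target, only a maximum of 12. So the texts are compared first.

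- *Reading A, evaluability.* Enrolment continues until enough usable concentration profiles through 24 hours are in hand, and 12 is a cap that leaves room for replacements and unusable profiles. This fits the pairing with completion, the replacement clause in Protocol 5 and the evaluable-concentration condition in Protocol 9.2. Selection does not depend on the values, and Protocol 9.5 holds.
- *Reading B, observed values.* Enrolment depends on the level or spread seen so far. Protocol 9.5 is then true only of a formal interim analysis.

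The visible text does not choose between them.

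**How large could the effect be under reading B?** The following inputs are assumptions, because the documents give none: lognormal data, true between-subject CV 40%, one look at 6 subjects, maximum 12. The log-scale standard deviation is s = sqrt(ln(1 + 0.40²)) = sqrt(ln 1.16) = 0.385.

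*Stopping on spread (stop if the observed log-scale variance is at or below its true value).* Let p be the chance of stopping at 6 and e the contribution of stopped trials to the mean variance ratio.

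- p = P(χ²₅ ≤ 5) = 0.584; e = P(χ²₇ ≤ 5) = 0.340.
- Mean reported log-variance over true = e + [5(1 − e) + 6(1 − p)]/11 = 0.340 + (3.300 + 2.495)/11 = 0.867.
- Reverse rule (stop if above): (1 − e) + [5e + 6p]/11 = 0.660 + (1.700 + 3.505)/11 = 1.133.
- By simulation, with the rule stated as an observed CV at or below 40%, the median reported CV is 36%; with the reverse rule it is 41%; at a fixed n of 12 it is 39%.
- Looks at 4 to 8 give 0.78 to 0.92 for the first rule and 1.08 to 1.22 for the reverse.

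*Stopping on level (stop if the geometric mean is at or above its true value).*

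- Shift on the log scale = 0.25 × s × sqrt(2/(6π)) = 0.25 × 0.385 × 0.326 = 0.0314.
- exp(0.0314) − 1 = +3.2%. The opposite rule gives exp(−0.0314) − 1 = −3.1%.
- For CVs from 30% to 70% and looks at 4 to 8, the upward shift runs from about 1% to 9%.

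*Stopping for reasons unrelated to the values (reading A).* Variance ratio 1.00, shift 0%.

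**Against what background?** Take a fixed 12 subjects with no stopping at all.

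- 95% factor for the geometric mean = exp(t(0.975, 11) × s/sqrt(12)) = exp(2.201 × 0.385/3.464) = 1.28.
- 95% range of observed over true log-variance = χ²₁₁ quantiles/11 = 3.82/11 to 21.92/11 = 0.35 to 1.99.

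A 3% shift sits inside a 28% margin, and mean ratios of 0.87 or 1.13 sit inside a range of 0.35 to 1.99. Separate simulations at CVs of 30%, 50% and 70% put the coverage of a nominal 95% interval for the geometric mean at 93.9% to 94.6% under the low-spread rule, and at about 95% under the level rule.

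**The case for a change.** The strongest case for a change is that the one rule fixing n cannot be reproduced from the text. The SAP, where such a rule would normally be settled, only repeats the protocol sentence. The sample-size and interim-analysis sections show no redaction, so the rule is not hidden in them. Protocol 9.2 has a phrase for evaluability that the sample-size sentence does not use. Calling the trial exploratory does not remove a reader's interest in how n was reached.

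Much of this stands as a remark on wording. The phrase is ambiguous, and the visible text states no minimum, look or criterion. Absence can be confirmed only for what is visible: parts of Protocol 4.1 and 6.1 are blacked out, as is a large block after SAP section 8, where any section 9 would fall.

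The argument does not reach the results. It needs reading B, a rule nobody has stated and a value-based stop, and even then the distortion is small beside sampling error.

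A second argument is that without a minimum n the comparison of intact with sprinkled capsules could rest on very few children. That imprecision comes from the size of the pilot, not from any tension between 9.1 and 9.5. At CV 40%, even the full 12 split evenly gives a 95% factor of exp(t(0.975, 10) × 0.385 × sqrt(2/6)) = 1.64 for the ratio between modes, and the plan intends no inference on it. Nor would a required count per mode be a mere edit. Mode follows a screening swallow test and the even split is only attempted, so such a count might be out of reach within 12.

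**Conclusion.** The concern does not call for a change. On the evaluability reading there is no conflict and no bias. On the observed-values reading Protocol 9.5 is loosely worded, but the descriptive summaries remain sound for a pilot that tests nothing and has no error rate to protect. The sizes are about 3% in the geometric mean and a median reported CV of 36% or 41% against 39%, compared with a 95% factor of 1.28 from sampling alone. They assume CV 40%, one look at 6 and simple stopping rules. Other assumed settings move the geometric mean by up to about 9% (CV 70%, look at 4), where the 95% factor at 12 is itself 1.49.

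The missing minimum, look time and criterion are detail that a study team running a trial of at most 12 children can supply in practice. SAP 7.1 already tabulates the numbers treated, discontinued and completing, and the assignment by mode, so the achieved n will be open to the reader. No endpoint, analysis or stated figure is shown to be wrong.
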